8.3 Lost to Follow-up

A participant will be considered lost to follow-up if he or she repeatedly fails to return for scheduled visits and is unable to be contacted by the study site; this term does not apply to missed visits.

The following actions must be taken if a participant fails to return to the clinic for a required study visit:

- The site must attempt to contact the participant and reschedule the missed visit as soon as possible and counsel the participant on the importance of maintaining the assigned visit schedule and ascertain whether or not the participant wishes to and/or should continue in the study.
- Before a participant is deemed lost to follow up, the investigator or designee must make every effort to regain contact with the participant (where possible, 3 telephone or email contacts and, if necessary, a certified letter to the participant's last known mailing address or local equivalent methods). These contact attempts should be documented in the participant's medical record.
- Efforts to regain contact should continue until the end of the participant's last scheduled visit.
- Only if contact with the participant is not regained by the end of the visit window of the last scheduled visit can the participant be considered lost to follow up.

9 SAFETY ASSESSMENT

9.1 Adverse Events

An AE is any untoward medical occurrence in a clinical investigation participant that occurs during any part of the clinical study, whether related to the investigational device or not. Pre-existing conditions are

not reported as AEs unless there has been a worsening in severity or frequency which cannot be attributed to the disease's natural history or progression.

For AEs, the event description, severity (See Appendix 1 for definitions), date of onset, treatment, outcome, and relationship to device will be collected on the AE eCRF. When reporting an AE, if a clinical diagnosis is available, the diagnosis should be reported instead of individual symptoms.

All procedure- and device-related AEs must be followed until resolution or stabilization (the investigator does not expect any further improvement or worsening of the event).

An Adverse Device Effect (ADE) is any adverse event that is considered possibly-related or related to the device. An ADE may occur at any time after exposure to the investigational device.

Determination of whether there is a reasonable possibility that the investigational device caused or contributed to an AE will be reported by the investigator and reviewed by the medical monitor.

Determination will be based on assessment of temporal relationships, biologic plausibility, association (or lack of association) with underlying disease, and presence (or absence) of more-likely cause.

9.1.1 Serious Adverse Event

A SAE is an event that:

- Led to a death
- Led to a serious deterioration in health resulting in
 - a life-threatening illness or injury
 - a permanent impairment of a body structure or body function
 - in-patient hospitalization (>24 hours) or prolongation of an existing hospitalization
 - requires medical or surgical intervention to prevent life-threatening illness or injury or permanent impairment of a body structure or body function
- Led to fetal distress, fetal death or a congenital abnormality or birth defect

Here, "life-threatening" refers to an event when the patient is at substantial risk of dying at the time of the adverse event, it does not refer to an event that hypothetically might have caused death if it were more severe; "permanent" is defined as irreversible impairment or damage to a body structure or function, excluding trivial impairment or damage.

For the purpose of this study, diagnostic endoscopy is not considered as "intervention" in the context of SAE. Planned hospitalization for a pre-existing condition is not considered as a SAE.

9.1.2 Serious Adverse Device Effect

An SADE is an SAE that is possibly related or related to the device.

9.1.3 Unanticipated Serious Adverse Device Effects

Unanticipated Serious Adverse Device Effects (UADE) are any serious adverse device effect which by its nature, incidence, severity or outcome has not been identified in any of study documents such as the investigational plan, investigator's brochure, Instruction for Use (IFU), or Informed Consent.

When an AE meets the definition of a UADE or that relationship is unknown, the investigator will report the event to sponsor within 24 hours but no later than five (5) working days after the investigator first learns of the effect and reports to the reviewing EC as required.

9.1.4 Abnormal Pancreatic Enzyme Levels

Changes in serum amylase, lipase levels post procedure should trigger assessment for potential pancreatic injury.

The diagnosis of acute pancreatitis requires two of the following three features³:

- Abdominal pain consistent with acute pancreatitis (acute onset of a persistent, severe, epigastric pain often radiating to the back)
- Serum lipase and/or amylase level at least three times greater than the upper normal limit
- characteristic findings of acute pancreatitis on imaging.

For all confirmed events of pancreatitis, the following additional information should be reported if available:

- Signs and symptoms of pancreatitis
- Specific laboratory test supporting a diagnosis of pancreatitis:
- Imaging performed and consistency with pancreatic disease
- Treatment for and complications of the event
- Relevant risk factors for pancreatic disease
- Family history of pancreatitis

Participants with an increase in pancreatic enzyme levels (>3 x ULN) post procedure should be followed until their levels return to the baseline level.

9.1.5 Hypoglycemia

Hypoglycemia is defined as follows (ADA 2020):

- Level 1 hypoglycemia is a blood glucose concentration 54–70 mg/dL (3.0–3.9 mmol/L).
- Level 2 hypoglycemia is a blood glucose concentration <54 mg/dL (3.0 mmol/L), which is typically the threshold for neuroglycopenic symptoms.
- Level 3 hypoglycemia is a clinical event characterized by altered mental and/or physical functioning that requires assistance from another person for recovery

Documented symptomatic hypoglycemia: An episode during which typical symptoms of hypoglycemia are accompanied by a measured plasma glucose concentration \leq 3.9 mmol/L (70 mg/dL).

Probable symptomatic hypoglycemia: An episode during which symptoms of hypoglycemia are not accompanied by a plasma glucose determination but that was presumably caused by a plasma glucose concentration \leq 3.9 mmol/L (70 mg/dL).

Blood glucose concentration may be determined by a laboratory test or capillary blood glucose measurement using a glucose meter and test strips. CGM alerts must be confirmed by blood glucose values.

Level 3 hypoglycemia is defined as **severe hypoglycemia** and should be reported as adverse event. Other non-severe hypoglycemia will be recorded on hypoglycemia eCRF.

To avoid duplicate reporting, all consecutive blood glucose values $\leq 70 \text{mg/dL}$ occurring within an 1-hour period may be considered to be a single hypoglycemic event.

9.2 Device Relationship (Causality)

Causality assessment is required for AEs (and SAEs) that occur during clinical investigations. The following terms will be used during this study:

- Related An AE that is directly and clearly related to the Investigational Device
- Possibly Related There is a reasonable likelihood that the event is due to the Investigational Device, as evidenced by the following:
 - There may be temporal association with the Investigational Device (e.g., within 24 hours of the DMR procedure)
 - The event, or level of severity of the event, is unlikely to be explained by other etiologies (known to be related to the study disease, patient's baseline medical condition, or concomitant medications)
- Unlikely Related The AE is not temporally related to the Investigational Device, or is known to be related to one of the following:
 - Morbidity associated with underlying medical condition
 - Anesthesia
 - Upper GI endoscopy
 - Concomitant medication
 - A relationship to the Investigational Device is not biologically plausible
- Not related The AE is definitely not related to the Investigational Device

9.3 Adverse Event Reporting

9.3.1 Sponsor Reporting Requirements

The Sponsor will conduct an evaluation of any reported UADEs and will report the results of this evaluation to the FDA, IRBs, and participating Investigators within 10 working days after first receiving notice of the event. In addition, if any of the stopping rules are triggered (Section 4.5), it will be reported to FDA, IRB, and participating investigators following the UADE reporting timeline.

9.3.2 Clinical Site Reporting Requirements

- All AEs and ADEs will be recorded by the investigator or designee on the eCRFs provided
- UADE or suspected UADE, or any event that can potentially trigger the stopping rules as described in Section 4.5, will be reported to the sponsor within 24 hours of knowledge of the event, followed by a written confirmation by the investigator within 5 working days
- Any other SAEs are to be reported to the sponsor within 36 hours
- The investigator at each site is ultimately responsible for reporting AEs, SAEs and UADEs to the IRB according to IRB requirements

10 MEDICAL MONITORING

Device relationship of the SAEs will be reviewed and adjudicated by an independent medical monitor who has relevant expertise and is not affiliated with the sponsor or the study site. The medical monitor may require additional explanatory or supportive documents, which may include source documents from the hospital, as needed, when reviewing the events. The medical monitor will also monitor the overall safety of the study and recommending appropriate actions to the sponsor, when necessary.

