2.5.2 Anticipated Adverse Events Associated with the DMR Procedure

Anticipated AEs associated with the DMR procedure may include, but are not limited to, the following:

- Complications associated with upper GI endoscopy, including but not limited to, aspiration of gastric contents, aspiration pneumonia
- Complications related to sedation and anesthesia
- Cardiac or respiratory arrest during endoscopy
- Cardiac arrythmia, muscle spasm, or electrical shock during the procedure
- Death
- Duodenal mucosal inflammation, erythema, erosion, ulcer, bleeding, perforation and their associated complications
- Duodenum motility disorder
- Duodenum stricture and/or obstruction, and their associated complications or interventions
- Excess reduction in oral intake, resulting in dehydration, ketoacidosis, and their associated complications
- GI symptoms post procedure, including nasopharyngeal pain, abdominal pain, cramps, abdominal discomfort, nausea, vomiting, diarrhea, and other GI symptoms
- Inability to endoscopically remove part or all of the device, which may result in the need for surgery
- Infection, systemic or of GI tract and their associated complications

- Injury to the area of ampulla, leading to biliary and/or pancreatic complications such as biliary obstruction, pancreatitis, etc.
- Injury to peripheral tissue and their associated complications, such as peripancreatic fluid collections, pseudocyst, pancreatic and peripancreatic necrosis, peri-duodenal inflammation or abscess, vascular injuries, pseudoaneurysm, etc.
- Interfere with absorption resulting in nutritional deficiencies
- Undesired metabolic response such as hypoglycemia
- Upper GI tract trauma, including sore or irritated throat, bleeding, perforation, and their associated complications

2.5.3 Residual Risks Associated with the Investigational Device, as Identified in the Risk Analysis Report

Endogenex has conducted extensive assessment of the potential risks associated with the device and its use through Hazard Analysis and FMEA (failure mode and effects analysis) per ISO 14971. A number of safeguards have been built into the device to mitigate risks. The risk assessment concludes that, when used as intended and with mitigation measures implemented, there are no unacceptable risks to the intended patient population.

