12.4.3 Primary Endpoint Analysis

The primary endpoint of the study is the proportion of participants experiencing one or more device- or procedure-related serious adverse events within 12 weeks post-procedure. The analysis will be performed using the ITT population, then tabulated and reported for each treatment arm and overall. Fisher's exact test will be used to assess differences which may be present between groups

Additionally, an overall summary of AEs will be provided including the number of events and percent of participants with any AEs, SAEs, and UADEs. For each type of event, the number of events and number and percent of participants with the event will be provided. Separate summaries of all adverse events will be summarized by seriousness and by relationship to device and procedure.

Only events occurring at or after the index procedure will be counted for the purpose of safety analysis. Events occurring prior to the index procedure will be considered as medical history.

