### 10.1.4. Summaries of Serious Adverse Events

The tables outline above will be repeated, restricted to just serious adverse events. All summaries of serious adverse events will be based on events that occurred during the study. Adverse events will be mapped to preferred terms and body systems using the Medical Dictionary for Regulatory Activities (MedDRA) coding dictionary. The number and percentage of patients experiencing 1 or more adverse events will be presented by preferred term using counts, percentages, and 2-sided 95% exact binomial confidence intervals. The relationship of the adverse event relative to the device and procedure will be presented separately. The number and percentage of patients experiencing 1 or more events will be presented by the event description using counts, percentages, and 2-sided 95% exact binomial confidence intervals.

- Table 14.3.7 entitled Overall Summary of Serious Adverse Events (ITT Population)
- Table 14.3.8 entitled Summary of Serious Adverse Events by Event Type (ITT Population)
- Table 14.3.9 entitled Summary of Post-Procedural Adjudicated Serious Adverse Events by Event Type and Relationship to the Study Device (ITT Population)
- Table 14.3.10 entitled Summary of Post-Procedural Adjudicated Serious Adverse Events by Event Type and Relationship to the Study Procedure (ITT Population)
- Table 14.3.10.1 entitled Summary of Post-Procedural Adjudicated Serious Adverse Events by Event Type and Relationship to the Study Device or Procedure (ITT Population)
- Table 14.3.11 entitled Summary of Serious Adverse Events Leading to Study Discontinuation (ITT Population)

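### The procedure half of the primary safety endpoint rests on an undefined, unadjudicated investigator grade, and two SAP tables labelled as adjudicated cannot be produced as labelled

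*Protocol*

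**What the plan says.** Protocol 12.4.3 defines the primary endpoint as "the proportion of participants experiencing one or more device- or procedure-related serious adverse events within 12 weeks post-procedure". SAP 9 and 9.1 use the same two-part definition, with a window to day 84, and code it as the variable DRPRSAE.

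On causality, the protocol speaks only of the device:
- Section 9.1, on the data recorded: "date of onset, treatment, outcome, and relationship to device will be collected on the AE eCRF".
- Section 9.2 is headed as device relationship, and its four grades are all worded against the investigational device. Its Unlikely Related grade reads "The AE is not temporally related to the Investigational Device, or is known to be related to one of the following", and the list that follows names anesthesia and upper GI endoscopy.
- Section 10, on independent review: "Device relationship of the SAEs will be reviewed and adjudicated by an independent medical monitor".

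Section 2.5.2 lists the anticipated adverse events of the DMR procedure. Among them are "Complications associated with upper GI endoscopy, including but not limited to, aspiration of gastric contents, aspiration pneumonia" and "Complications related to sedation and anesthesia".

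The SAP goes further. Section 4.2 lists two CRF items, AEDREL (relationship to device) and AEPREL (relationship to procedure), each with four levels and no definitions. Section 10.1.1 confirms that both relationships are obtained for each event. Section 10.1.4 then plans Table 14.3.10, "Summary of Post-Procedural Adjudicated Serious Adverse Events by Event Type and Relationship to the Study Procedure", and Table 14.3.10.1, "Summary of Post-Procedural Adjudicated Serious Adverse Events by Event Type and Relationship to the Study Device or Procedure".

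**The concern.** The endpoint joins two kinds of event with an *or*, but only one kind has defined grades and an independent adjudicator. The procedure part is meant to catch what the device part leaves out: harm from the endoscopy, the sedation or the anesthesia of the index session. For those events the protocol's only defined scale gives Unlikely Related. That is right for the device and says nothing about the procedure.

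Two things are at stake. First, sites must grade AEPREL without being told what the procedure includes or what separates possibly from unlikely. A site that carries the Section 9.2 wording over to AEPREL would grade an anesthesia complication as unlikely; a site that reads procedure as the whole index session would not. In an open-label study this is the half of the endpoint most exposed to differences in judgement. Second, the SAP promises adjudicated procedure relationship in two tables, and no step in either document produces it.

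**Working it through.** The plan states no figure to reproduce; Protocol 12.2 says power calculations are not relevant here. The check is a comparison of the text, followed by an illustration of size.

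**Step 1. What each half of the endpoint has behind it**

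| Element | Device | Procedure |
|---|---|---|
| Part of the primary endpoint (Protocol 12.4.3; SAP 9) | Yes | Yes |
| Recorded on the CRF (SAP 4.2, 10.1.1) | Yes, AEDREL | Yes, AEPREL |
| Grades defined (Protocol 9.2) | Yes | No |
| Adjudicator assigned (Protocol 10) | Yes, medical monitor | No |
| SAP table titled as adjudicated (SAP 10.1.4) | 14.3.9, 14.3.10.1 | 14.3.10, 14.3.10.1 |

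Three tables carry the adjudicated label with a relationship breakdown. Two of the three, 14.3.10 and 14.3.10.1, need a procedure adjudication. A Clinical Events Committee appears in the SAP's abbreviation list but is given no role anywhere.

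**Step 2. Which source feeds the primary count**

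SAP 9.1 does not say whether DRPRSAE uses CRF or adjudicated grades. SAP 4.2 lists only CRF items, and the primary tables are supported by the Adverse Events listing, so CRF grades are the natural reading. Nor does SAP 9.1 say which grades count as related. Protocol 9.1.2 treats possibly related as sufficient for a serious adverse device effect, which points to Definitely or Possibly related.

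**Step 3. How many anticipated events are of this kind**

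Section 2.5.2 has 17 entries. Three name endoscopy, sedation or anesthesia as the source or setting: endoscopy complications, sedation and anesthesia complications, and cardiac or respiratory arrest during endoscopy. This counts entries in a list; it does not measure risk.

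**Step 4. What one classification does to the result**

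Assume one participant whose only qualifying SAE is not device-related, so that the procedure grade alone decides whether the participant counts. No event rate is assumed. Exact (Clopper-Pearson) 95% limits:
- x = 0: lower 0, upper 1 − 0.025^(1/n). For n = 20: 1 − 0.025^(1/20) = 16.8%.
- x = 1: lower 1 − 0.975^(1/n), upper the 97.5% quantile of Beta(2, n − 1). For n = 20: 0.1% and 24.9%.

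| Group | Not counted | Counted |
|---|---|---|
| All, n = 20 | 0% (0 to 16.8%) | 5.0% (0.1 to 24.9%) |
| One voltage group, n = 10 | 0% (0 to 30.8%) | 10.0% (0.3 to 44.5%) |
| 600 V double treatment, n = 7 | 0% (0 to 41.0%) | 14.3% (0.4 to 57.9%) |
| 600 V single treatment, n = 3 | 0% (0 to 70.8%) | 33.3% (0.8 to 90.6%) |

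Group sizes are from Protocol 12.2 and SAP 3.

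**The case against.** The strongest reply is that the endpoint works as written. AEPREL is on the CRF, the SAP counts device-related or procedure-related events, and the natural source is the CRF. This stands, and it rules out one tempting inference: that an aspiration pneumonia caused by the endoscopy would fall out of the primary count. It would do so only if AEPREL were ignored, and nothing in the SAP suggests that.

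A reader might also infer that Tables 14.4.1 and 14.3.10.1 report the same quantity and could contradict each other. They do not. The primary table covers SAEs to day 84, while 14.3.10.1 is by event type over the whole study, so the two can properly differ.

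A third inference is that procedure attribution gets no independent scrutiny. The documents do not support that either. The monitor reviews SAEs, may ask for source documents and watches overall safety (Protocol 10). The DSMB reviews cumulative data and any event that triggers a stopping rule (Protocol 11). This is real oversight, but it does not assign a procedure grade to an event.

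The word adjudicated may also be left over from another plan; SAP 10.1.1 speaks of randomized groups in a study that has none. That is plausible. Even so, the titles must be corrected or made true. Finally, the intervals in the working would look the same for any disputed SAE, so they show the sensitivity of a small study and do not measure a bias.

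**Conclusion.** The point holds as a limited one. The protocol defines and adjudicates device relationship only. The procedure half of the sole primary endpoint therefore depends on an investigator grade with no definitions and no adjudication, and Tables 14.3.10 and 14.3.10.1 cannot be produced as labelled.

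The size depends on events not known from the documents. If no SAE is related to the procedure alone, or if investigator and monitor would agree on each one, the primary count does not change. Each participant classified differently moves the overall proportion by 5 percentage points (1/20), and by 33.3 points in the 3-patient group. Adjudication could raise or lower the count.

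The consequence is bounded. There is no formal hypothesis (SAP 9) and no success threshold, and SAEs are also tabulated without regard to relationship. The change is still worth making, because the person who would do the work already reviews every SAE.

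**What to change.** Before database lock:

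1. Have the same independent medical monitor adjudicate relationship to the device and to the procedure for every SAE, including those already reviewed for device relationship.
2. In Protocol 9.2 or SAP 4.2, state that procedure means the index session including its endoscopy and anesthesia, and define the four AEPREL grades in parallel with the device grades.
3. In SAP 9.1, define DRPRSAE once: an SAE within the stated day-84 window whose adjudicated device or procedure relationship is Definitely or Possibly related.
4. Report the count on the investigator's grades beside the adjudicated count, so that any event added or removed by adjudication is visible.

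If adjudication is not extended, remove the word adjudicated from the titles of Tables 14.3.10 and 14.3.10.1, and state in SAP 9.1 that the investigator's grades drive the primary count.

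The cost is one extra judgement per SAE and a few sentences of text. No new staff, visits or tests are needed.

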11 DATA SAFETY MONITORING BOARD

The DSMB is composed of independent physicians who are not participating in the study and will not be affiliated with the sponsor, the Investigators, or the investigational sites. The DSMB will review the study on a periodic basis and per requirements defined in Section 4.4 and 4.5, is responsible for making recommendations regarding any safety or compliance issues throughout the course of the study and may recommend to the sponsor to modify or stop the study. However, all final decisions regarding study modifications or study termination rest with the sponsor.

Cumulative safety data will be reported to the DSMB and reviewed on an ongoing basis throughout enrollment and follow-up periods to ensure subject safety. DSMB will also review individual events when stopping rules (Section 4.5) are triggered. Every effort will be made to allow the DSMB to conduct an unbiased review of subject safety information. All DSMB reports will be made available to the FDA upon request, but will otherwise remain strictly confidential.

DSMB will meet according to the following schedule:

- a. Initial meeting will commence before the study start or shortly after the study start.
- b. DSMB will convene as often as necessary but at a minimum at the schedule described in Section 4.4.
- c. Additionally, a DSMB meeting may be requested by DSMB member, the Sponsor, or IRB at any time to discuss safety concerns if it arises.

DSMB recommendation may include the following

- Continue study without modification
- Continue study with conditions
- Suspend or terminate the enrollment
- Permit re-commencement of enrollment following a suspension

